**February, 2018**

## Introduction

Overweight and obesity are public health problems across the world. In 2016 the World Health Organization (WHO) estimated that over 1900 million adults were diagnosed as overweight or obese (1). Currently, these pathologies are associated with the risk of developing pathologies such as insulin resistance, Type 2 Diabetes Mellitus(T2DM) and Metabolic Syndrome (2).

These pathologies result from the interaction between many factors, mainly poor alimentary habits and a sedentary lifestyle (2-4). The high consumption of simple carbohydrates and sugar sweetened beverages (SSBs), like soft drinks, juices and flavored water, is considered one of the main factors that contribute to the increase in incidence and prevalence of overweight and obesity. A high consumption of simple carbohydrates promotes an increase glucose concentrations in blood, which facilitates the formation of triglycerides that are subsequently stored in adipose tissue (2, 4, 5).

Mexico is the Latin American country with the highest consumption of SSBs. It was estimated that the intake per person was 384 SSBs per year (6). The exact figures of the population that consumes ASBs are not known. However, an increase in the consumption of products containing artificial sweeteners (ASs) was reported (7, 8). In Mexico, more than 70% of the adult population has been diagnosed as overweight or obese (1).

To decrease the caloric intake attributable to SSBs, the food industry promotes the commercialization of ASBs (9). These products have the same organoleptic features than SSBs, with the perks of having a minimum or no caloric contribution at all, not

affecting the energy metabolism (10). For this reason, in Mexico the official treatment guidelines for overweight and obesity recommend its use as part of the nutritional treatment (11).

Nonetheless, recent studies relate the consumption of ASBs with a deregulation of the metabolic homeostasis, promoting physiological modifications (12). In a study conducted by Duran, *et. al.* aiming to evaluate the effect of the reduction of SSBs and ASBs, concluded that the reduction in the consumption of these beverages decreased weight and body fat (13). On the other hand, Madjad, *et. al.* reported a decrease in body weight of women with type 2 diabetes mellitus after substituting the consumption of ASBs, for water (14). Some cohort studies reported an association between the consumption of ASBs and the increase in body weight and waist circumference (4, 15). Likewise, it was reported that ASs increased glucose and insulin concentrations in blood, which is detrimental to health, especially in population with a pre-existing risk of developing non-infectious diseases, such as overweight and obesity (12, 16-18).

While population increases the consumption of ASBs, the prevalence of overweight and obesity increased too. To contribute to the knowledge on the effect of these substances in the human body, we evaluated the effect of reducing the consumption of ASBs in overweight and obese young adults.

## **Objective**

Evaluate the effect of restriction ASBs consumption on the metabolism in overweight and obese young adults

## **Hypothesis**

The restriction of ASBs in young people who consume them and who present overweight and obesity, decrease an anthropometric data, and biochemical markers.

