### **- Randomization and intervention procedure**

All the volunteers that will meet the inclusion criteria will sign the informed consent before the study started. The volunteers will randomly allocate in control or intervention group (1:1 allocation ratio to each group) in blocks of 2 by using Microsoft Office Excell. Nobody involved with data acquisition will have access to de assignment of the subjects. Once randomly assigned, a blood sample and anthropometric variables will take to establish basal data. Participants will interview to know, caloric intake (24-h food recall), consumed portions and beverage consumption (Food frequency questionnaire). The intervention group is not allowed to consume ASBs, however they are allow consuming products that did not contain ASs in their formulae. For the control group ASBs consumption are not modified. Both groups continue the normal food habits.

Anthropometric measures, 24-h food recall and food frequency questionnaire data will collect at week 6 and 12. Blood sample will take once more at study week 12. In order to categorize the physical activity a previously validated questionnaire will apply, the physical level are divide in low, moderate and high.

- **Study population**

Young overweight or obese students between 19 and 27 years old with normally consumption of ASBs

- **Sample**

It is a probabilistic, stratified sampling that is made from the overweight and obese population who consume ASBs.

The data for obtaining the sample will be collected from the questionnaires that will be applied to the students in which we will know who consume ASBs.

- **Statistic**

They will be analyzed with the statistical program SPSS 21. With a two-way analysis of variance ANOVA or T-student test with repeated measures. And the variables will be correlated.

- **Ethical and biosecurity considerations**

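### The hypothesis names two outcome classes but no deciding outcome, and the analysis text permits a before-after t-test that does not use the randomised control

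*Protocol*

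**What the plan says.** The Objective section reads "Evaluate the effect of restriction ASBs consumption on the metabolism in overweight and obese young adults" and names no variable. The Hypothesis section predicts that restriction will "decrease an anthropometric data, and biochemical markers". No section lists the body measurements or blood analytes, ranks them, or calls one primary. Weight, body fat, waist circumference, glucose and insulin appear only in the Introduction, as findings of earlier studies.

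Under Design and methods, the trial is randomised 1:1 to 12 weeks without ASBs or to a control group. On the control: "For the control group ASBs consumption are not modified". On diet otherwise: "Both groups continue the normal food habits".

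Both classes are measured at baseline. After that, "Anthropometric measures, 24-h food recall and food frequency questionnaire data will collect at week 6 and 12", while for blood, "Blood sample will take once more at study week 12".

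Apart from naming the software and adding that variables will be correlated, the Statistic item consists of one choice: "With a two-way analysis of variance ANOVA or T-student test with repeated measures".

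**The concern.** There are two linked gaps.

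First, a reader cannot tell which result would confirm or refute the hypothesis. The classes are open-ended, and anthropometry has two post-baseline visits with neither marked as the deciding one.

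Second, the two permitted tests can answer different questions. A two-way ANOVA can be read as arm by time, and its interaction then compares the arms. A t-test for repeated measures is, in ordinary usage, the paired t-test, which compares before with after in one group. Used that way it sets the control arm aside. Anything that lowers a measurement in both arms, such as season, regression to the mean, or the effect of being weighed and interviewed about diet three times, would then be reported as an effect of restriction. The control arm is there to remove such shared change, and only a between-arm comparison does so.

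**Working it through.** The protocol states no sample size, alpha, SD, effect size or number of outcomes, so there is no figure of its own to reproduce. What follows is illustration under stated assumptions.

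**Assumed inputs.** Two-sided 5% tests, so 2.5% in the direction of a decrease; 20 or 50 participants per arm; normally distributed changes; no intervention effect; both arms falling by the same d = 0.1, 0.2 or 0.3 SD of the within-person change.

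**Step 1: paired test in the intervention arm alone.** The statistic is noncentral t with n − 1 degrees of freedom and noncentrality d√n. The false-decrease rate is p = P(T > t₀.₉₇₅), taking a fall as positive.
- n = 20: d√n = 0.45, 0.89, 1.34, giving p = 0.062, 0.133, 0.246.
- n = 50: d√n = 0.71, 1.41, 2.12, giving p = 0.103, 0.283, 0.548.
- d = 0: p = 0.025.

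**Step 2: a significant decrease in the intervention arm and none in the control.** With no intervention effect the arms are independent and share the same p, so the rate is p(1 − p).
- n = 20: 0.062 × 0.938 = 0.058; 0.133 × 0.867 = 0.115; 0.246 × 0.754 = 0.185.
- n = 50: 0.103 × 0.897 = 0.092; 0.283 × 0.717 = 0.203; 0.548 × 0.452 = 0.248.

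This rate cannot exceed 25%, because p(1 − p) is at most 1/4.

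**Step 3: between-arm test on change.** The shared fall cancels in the difference, so the false-decrease rate is 2.5% whatever d is. In simulation with 20, 30 and 50 per arm and shared falls of 0 to 0.5 SD, the two-sided rate stayed between 4.8% and 5.1%.

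| Rule for claiming a decrease | 20 per arm, d = 0.1 / 0.2 / 0.3 | 50 per arm, d = 0.1 / 0.2 / 0.3 |
|---|---|---|
| Intervention arm significant | 6% / 13% / 25% | 10% / 28% / 55% |
| Intervention significant, control not | 6% / 12% / 19% | 9% / 20% / 25% |
| Between-arm difference in change | 2.5% | 2.5% |

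**Step 4: how much does the open hypothesis inflate error by itself?** The hypothesis joins the classes with an *and*. Assume five markers per class, no effect anywhere, and a claim that needs at least one significant decrease in each class. With independent markers, one class gives 1 − 0.975⁵ = 0.119, and both give 0.119² = 0.014. With equal correlation of 0.5 or 0.9 across all markers, numerical integration gives 0.039 and 0.038. One named outcome gives 0.025.

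**Step 5: which contrast?** Blood has two time points, so a between-arm t-test on change is the same test as the arm-by-time interaction. Anthropometry has three, so the overall interaction has (2 − 1) × (3 − 1) = 2 degrees of freedom and does not isolate week 12. The week-12 contrast has to be named.

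**The case against.** The strongest reply is that the Statistic item is compressed, translated English and has a reading that fits the design. The words about repeated measures may govern both tests: a repeated-measures ANOVA for anthropometry with three visits, and a between-arm t-test on change for blood with two. Nothing says that a within-arm result will count as the treatment effect, and an SAP that is not shown could settle the contrast. This is possible, but the text does not state it. As written, the paired test is an allowed alternative, and an SAP would have to override that wording. Naming a primary outcome is the protocol's job in any case.

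A second reply is that the step 1 rates treat the control arm as if nobody looked at it. That is fair, and step 2 gives the lower figures. They still exceed 2.5% by a wide margin.

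Three stronger readings are tempting, and the documents support none of them:
- A reader might infer that the trial will be analysed within arms. The protocol only permits this.
- A reader might infer serious multiplicity from the two open classes. Step 4 shows that the hypothesis read literally adds little. A larger figure needs one class to improve truly and any single marker to carry the other, a rule the protocol does not state. Alpha and multiplicity handling may also sit in an SAP.
- A reader might infer, from the protocol date of "February, 2018" against a study period starting in February 2017, that the outcome was left open after results were seen. The dates do not show that anyone had examined outcome data by arm.

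**Conclusion.** The concern holds in a limited form. No deciding outcome is named, and one of the two permitted tests, in its ordinary meaning, makes no use of the randomised control. If that test were used, a modest shared decline could produce a false claim several times more often than the 2.5% of a between-arm test. The factor depends on assumed arm sizes, an assumed shared fall of 0.1 to 0.3 SD, and whether the control arm's own result is also considered. None of these inputs comes from the protocol, so the rates show the direction and scale of the risk and do not estimate what happened in this trial. If the intended analysis was already between arms, the correction only makes that explicit.

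**What to change.** In the Statistic item, replace the choice of tests with one: the between-arm difference in change from baseline to week 12. For anthropometry this is the week-12 arm-by-time contrast; for blood markers a between-arm t-test on change is equivalent. Add that a before-after test within an arm does not support the hypothesis.

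In the Hypothesis section, name one primary outcome at week 12. The choice is the sponsor's and should be made before outcome data are examined by arm. Label all other measures, the week 6 results and the correlations secondary or exploratory.

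The cost is a paragraph of wording and no new data. The downside is that other markers can no longer carry the headline claim.

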## **Design and methods**

### **- Study Design**

This study is a single-blind randomized clinical trial it will perform at the University of Veracruz, Veracruz, Mexico, between February 2017 to October 2018. Young adults students of the University of Veracruz will randomly allocate to a 12-week no consumption of ASBs intervention or control group.

### **- Randomization and intervention procedure**

All the volunteers that will meet the inclusion criteria will sign the informed consent before the study started. The volunteers will randomly allocate in control or intervention group (1:1 allocation ratio to each group) in blocks of 2 by using Microsoft Office Excell. Nobody involved with data acquisition will have access to de assignment of the subjects. Once randomly assigned, a blood sample and anthropometric variables will take to establish basal data. Participants will interview to know, caloric intake (24-h food recall), consumed portions and beverage consumption (Food frequency questionnaire). The intervention group is not allowed to consume ASBs, however they are allow consuming products that did not contain ASs in their formulae. For the control group ASBs consumption are not modified. Both groups continue the normal food habits.

Anthropometric measures, 24-h food recall and food frequency questionnaire data will collect at week 6 and 12. Blood sample will take once more at study week 12. In order to categorize the physical activity a previously validated questionnaire will apply, the physical level are divide in low, moderate and high.

- **Study population**

Young overweight or obese students between 19 and 27 years old with normally consumption of ASBs

- **Sample**

It is a probabilistic, stratified sampling that is made from the overweight and obese population who consume ASBs.

The data for obtaining the sample will be collected from the questionnaires that will be applied to the students in which we will know who consume ASBs.

- **Statistic**

They will be analyzed with the statistical program SPSS 21. With a two-way analysis of variance ANOVA or T-student test with repeated measures. And the variables will be correlated.

- **Ethical and biosecurity considerations**

According to the Regulation of the General Health Law on Health Research, which was enacted in 1984 by Miguel de la Madrid in his third article, research for health includes the development of actions that contribute; to the knowledge of the biological and psychological processes of humans, to the knowledge of the links to the causes of illness, the medical practice and the social structure, to the prevention and control of health problems, to the knowledge and evaluation of the harmful effects of health environment, to the study of the techniques and methods that are recommended or used for the provision of health services, and to the production of supplies for health.

According to article 13 of this law, in any investigation in which the human being is subject to the study, the criterion of respect for their dignity and the protection of their rights and welfare must prevail.

According to article 16 in the investigations of human beings the privacy of the individual subject to the investigation will be protected, identifying it only when the result requires it and this authorizes.

According to article 17 in its second section, this research is considered as minimal risk since the risk of data is used through common procedures, physical or psychological diagnostic tests or routine treatments.

For what subject to the law, the informed consent letter will be provided to the research prospectus, which will be delivered prior to the application of the questionnaire. For the application of the questionnaire will pass through each classroom of the Faculty of Nutrition and Biochemistry of the Veracruz University Veracruz campus, which will be carried out after authorization by the authorities of each faculty. Likewise, the subject will be given a clear and concise explanation of the objectives of the research, the benefits, the inconveniences or risks expected the procedures that will be used, its purpose and the previous investigations that have been carried out on the subject, as well as those that arise during the time of the study. This process will be in charge of the main researcher of the project.

The prospect should be aware that he is at liberty to withdraw his consent at any time, and that the information collected during the investigation will be used only by the research group who will replace his name with a code to guarantee the confidentiality of the data.

Only the principal investigator of this project acquires the commitment with the participating subjects to continue with a nutritional follow-up during the 3 months after the end of the study, which includes a personalized nutritional plan, which will be obtained from anthropometric measurements. In the same way, the researcher commits to provide the results of the analysis of the biochemical values that are carried out at the beginning and at the end of the project.

To present the results obtained in the research to the participating subjects and the Health Services Studies Center, a summary of the most relevant data of the study signed by the main researcher will be made, which will be sent to them by email or will deliver them in a personal way according to the preference of the subject and the institution.

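### Fixed blocks of 2 let up to half of the allocations be known in advance if participants are allocated one by one and earlier assignments are seen; no bias is shown, and a less predictable method costs little

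*Protocol*

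**What the plan says.** Under Randomization and intervention procedure, the protocol fixes a 1:1 ratio "in blocks of 2 by using Microsoft Office Excell". No variation in block size is mentioned. The same section adds one safeguard: "Nobody involved with data acquisition will have access to de assignment of the subjects". On timing it says "All the volunteers that will meet the inclusion criteria will sign the informed consent before the study started", and it places the baseline blood sample and anthropometry after assignment.

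The intervention is an instruction: "The intervention group is not allowed to consume ASBs". The participant and whoever gives the instruction therefore know the arm. Study Design calls the trial single-blind without naming the blinded party.

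On recruitment, Sample says "It is a probabilistic, stratified sampling that is made from the overweight and obese population who consume ASBs" and "The data for obtaining the sample will be collected from the questionnaires". Ethical and biosecurity considerations describes classroom visits ("For the application of the questionnaire will pass through each classroom") and makes the main researcher responsible for the information and consent process.

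The analysis, under Statistic, is described as "With a two-way analysis of variance ANOVA or T-student test with repeated measures". The study window is February 2017 to October 2018, and the document is dated February 2018.

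**The concern.** A fixed block of 2 is the most predictable permuted block there is. Three conditions make an allocation knowable:

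- volunteers are allocated one by one;
- the observer sees earlier assignments;
- the observer knows the block size, which is printed in the protocol.

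A fourth, discretion over who enters when, is needed only to act on the knowledge. Someone in that position could, even without meaning to, bring a volunteer forward or hold one back according to the arm that comes next. Randomisation is meant to remove exactly that selection bias. The protocol neither establishes nor rules out the conditions on sequence, sight of assignments and discretion.

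**Working it through.** The protocol states no predictability figure, sample size or power, so there is no figure of its own to reproduce.

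**1. Predictability (exact).** In a 1:1 block of 2 the first assignment has probability 1/2 and the second is determined.

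- Determined share for N allocations: floor(N/2)/N. This is 50% for even N and slightly less for odd N (N = 51: 25/51 = 49.0%).
- Best-guess rate: (0.5 + 1)/2 = 75%.

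For comparison, all permuted blocks were enumerated, assuming known size and full sight of earlier assignments. The 4/6/8 row was simulated for N = 40, 60 and 100, with an observer who knows the menu of sizes but not the size of each block.

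| Blocks | Determined | Guessable |
|---|---|---|
| 2 | 50.0% | 75.0% |
| 4 | 33.3% | 70.8% |
| 6 | 25.0% | 68.3% |
| 8 | 20.0% | 66.6% |
| random 4/6/8, sizes hidden | about 2.3% | about 68% |

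**2. Possible effect on the error rate (assumption-based).** Assumed: 20, 30 or 50 per arm; a gap of η SD between the volunteers steered to one arm and to the other (0.3 or 0.5); baseline to follow-up correlation ρ of 0.8 to 0.98; equal variances. With blocks of 2, half of each arm is open to steering, so the spurious difference between arms is 0.5·η. The two-sided 5% rejection rate comes from the noncentral t with 2n−2 degrees of freedom and noncentrality d·√(n/2), where d is the spurious difference in SD units.

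*A. Steering on baseline level, change analysed.* The shift in change is 0.5·η·(ρ−1), and the SD of change is √(2(1−ρ)). At η = 0.5 and ρ = 0.8, |d| = 0.25 × 0.2/√0.4 = 0.079. Across n and ρ, the false-rejection rate is 5.0 to 5.6% at η = 0.3 and 5.1 to 6.8% at η = 0.5.

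*B. Steering on something that predicts change.* Here d = 0.5·η, and at η = 0.5, d = 0.25. With n = 50 the noncentrality is 0.25 × √25 = 1.25.

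*C. As B at η = 0.5, but only a share v of the first-of-pair assignments is seen.* Here d = 0.5·v·η.

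| Scenario | n = 20 | n = 30 | n = 50 |
|---|---|---|---|
| B, η = 0.3 | 7.5% | 8.8% | 11.5% |
| B, η = 0.5 | 12.0% | 15.9% | 23.6% |
| C, half seen | 6.7% | 7.6% | 9.5% |
| C, a quarter seen | 5.4% | 5.7% | 6.1% |

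Simulation with 40,000 trials per cell agrees (B at η = 0.5: 11.6, 15.7 and 23.1%).

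**3. Effect of changing the method.** The multiplier of η is 2 × (guess rate) − 1 when the enroller acts on best guesses. It is 0.50 for blocks of 2 and about 0.36 for hidden 4/6/8 blocks, which brings B at η = 0.5 down to 8.6, 10.5 and 14.5%. If the enroller acts only on certainties, the multiplier falls from 0.50 to about 0.02 and the rate is 5.0%. One batch gives zero.

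**The case against.** The strongest reply is that only the block size is stated, and it does no harm unless conditions on which the text is silent also hold. Several passages point towards the harmless reading. Consent before the study starts, a probabilistic sample from a questionnaire-based frame and the classroom visits all fit a completed list allocated in one batch. Recruitment uses a questionnaire, so the bar on those acquiring data may well extend to recruiters. No passage says that the main researcher sees assignments. Baseline is measured only after allocation, so an enroller would have screening impressions alone to steer by. Concealment matters more than block size: varying blocks lower the guess rate only from 75% to about 68%, and if earlier assignments are truly hidden, blocks of 2 cannot be exploited either. A randomisation procedure that is not shown may settle all of this.

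Most of that stands, and it limits the point to a conditional weakness. It does not remove it. The wording fits batch allocation without stating it, and a window of about 20 months for a 12-week intervention leaves room for staggered entry, though it does not prove it. The masking sentence does not plainly cover whoever consents or instructs volunteers. The block size is a stated choice, and its one evident benefit, tight balance, is small.

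A reader might infer that half of the allocations were in fact known, or that the false-positive rate is 12 to 24%. The document supports neither. The first needs sequential allocation and sight of earlier assignments. The second also needs control over entry, the assumed arm sizes and steering of 0.5 SD on a predictor of 12-week change.

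**Conclusion.** The point holds as a minor, conditional design weakness. The 50% and 75% figures are exact for an observer of sequential allocation who sees earlier assignments and knows the block size. Whether anyone is in that position cannot be determined from the protocol. The resulting bias is unknown: zero under batch allocation, near nominal in scenario A, and material only in scenario B, whose inputs are all assumed. Scenario A also depends on reading the planned repeated-measures analysis as a comparison of change. The case for acting is that a predictable method can be replaced cheaply, not that the results are biased.

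**What to change.** For participants not yet allocated, replace the blocks of 2 with one of the following:

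1. One randomisation of the complete consented list, half to each arm. This removes the predictability. The cost is waiting until the list is complete.
2. Randomly varying blocks (for example 4, 6 and 8) of undisclosed size, with the list kept from those who recruit and each assignment released only after consent. The concealment is essential here, since varying blocks alone leave about 68% guessable. The cost is a possible arm imbalance of up to 4 if recruitment stops mid-block, against at most 1 now. In simulation for totals of 40 to 100, even totals gave 0 in about 73%, 2 in 27% and 4 in 0.3%; odd totals gave 1 in 96% and 3 in 4%. With 40 participants, an 18/22 split costs 1 − 4·18·22/40² = 1% of efficiency.

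Either can be done with existing staff. The document is dated a year into the study window, so some participants may already have been allocated, and the change cannot cover them. For them, report whether allocation was batched or sequential, how assignments were released and who saw them. If it was one batch, a sentence saying so closes the point.

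### Basal data are taken after random assignment and nothing withholds the arm from participants until they are complete, so self-reported basal intake could depend on the arm (possible, not shown)

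*Protocol*

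**What the plan says.** The Protocol, under Randomization and intervention procedure, gives this order: consent, allocation 1:1, then baseline. On the baseline it says: "Once randomly assigned, a blood sample and anthropometric variables will take to establish basal data". The next sentence covers intake: "Participants will interview to know, caloric intake (24-h food recall), consumed portions and beverage consumption (Food frequency questionnaire". The restriction comes after that: "The intervention group is not allowed to consume ASBs". The later visits are given as "Anthropometric measures, 24-h food recall and food frequency questionnaire data will collect at week 6 and 12", with blood taken again at week 12 only.

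On masking, Study Design says "This study is a single-blind randomized clinical trial" and does not name the blinded party. The only provision that describes any masking is "Nobody involved with data acquisition will have access to de assignment of the subjects". The document does not say when participants learn their arm.

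Three other places bear on the point:
- Sample: ASB consumers are identified from "questionnaires that will be applied to the students in which we will know who consume ASBs".
- Statistic: the analysis is "With a two-way analysis of variance ANOVA or T-student test with repeated measures", without naming the variables it applies to.
- Ethical and biosecurity considerations: participants have the objectives of the research explained to them.

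**The concern.** A baseline is useful in a randomized comparison because it cannot depend on the arm. Taking it before allocation secures this. Taking it after allocation secures it only if whoever produces the value does not yet know the arm. For blood and anthropometry, that is largely the masked staff. For the 24-h recall and the food frequency questionnaire, it is the participant.

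A participant who has heard the aims of the study and has just been told to give up ASBs may report past intake differently from one told to carry on as usual. Masking the interviewer does not prevent this.

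At stake is the basal value of reported beverage and calorie intake and, if change in intake is analysed, the between-arm comparison of that change.

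**Working it through.** **Order of events.** The Protocol gives no figure that depends on this point, so there is none to reproduce. The first step is to read the sentences together.

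1. Basal blood and anthropometry: after assignment, stated in words.
2. Basal intake interview: placed after assignment by its position in the text. The same instruments recur at weeks 6 and 12, so this interview is the basal one. The sentence itself carries no time marker.
3. Disclosure of the arm to the participant: not stated. The restriction is described after the interview, which is compatible with later disclosure but does not fix it.
4. Masking: covers data collectors. It limits observer bias in measurements but does not cover what an informed participant reports.

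So the text permits the arm to be known at the basal interview and does not say that it is.

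**How a basal shift would carry through.** Assume no true effect on intake. Let d be the between-arm difference in reported intake at baseline due only to knowing the arm, and f the same at weeks 6 and 12 (taken as equal for simplicity). The between-arm differences at weeks 0, 6 and 12 are then (d, f, f).

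- Week 6 minus baseline: f - d
- Week 12 minus baseline: f - d
- Week 12 minus week 6: f - f = 0
- Direct comparison at week 6 or week 12: f

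If the basal data are complete before disclosure, the differences are (0, f, f). The change from baseline is then biased by f, and the direct comparison still by f.

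**When the reorder lowers the absolute bias in change.** The condition is |f| < |f - d|. Squaring gives f² < f² - 2fd + d², so 2fd < d². For d not equal to 0, this means f/d < 1/2.

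| f/d | Bias in change, present order (units of d) | Bias in change, after reorder (units of d) |
|---|---|---|
| -1 | -2 | -1 |
| 0 | -1 | 0 |
| 0.5 | -0.5 | +0.5 |
| 1 | 0 | +1 |

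The reorder removes d and never f. With a reporting shift that persists unchanged (f = d), the present order happens to cancel it in the change and the reorder does not. If participants in fact learn their arm after the basal interview, d = 0 and both orders give the same result. The document supports no value for d or f, so the table shows a range of assumptions and not an estimate.

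**The case against.** The strongest reply is that the harm is inferred. The sentence with the explicit time marker covers only blood and anthropometry, which are objective and taken by masked staff. The interview is placed after assignment by text order, and the same text order puts the restriction after the interview. The natural sequence may therefore be assign, measure, interview, then inform, in which case d = 0. This stands, and it is why the point is worded as a possibility. It does not dispose of the point, because an order that permits the problem is written down and nothing in the text closes it.

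A second reply is that the benefit of the reorder is not demonstrated, since it lowers the bias in change only when f/d < 1/2. This also stands. The case for the reorder is that a basal value should not be able to depend on the arm; it is not a promised reduction in bias.

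A reader might infer more than the document supports:
- **That basal intake is biased.** No sentence has a participant knowing the arm at the interview.
- **That the main results are compromised.** The Hypothesis concerns anthropometric and biochemical measures, which are barely affected if taken promptly after assignment. The interval is not stated.
- **That the trial's adherence measure is compromised.** The Protocol never presents intake as a measure of adherence.
- **That the shift enters the planned analysis.** The Statistic paragraph does not say that change in intake will be tested, so this consequence is conditional.
- **That eligibility is affected.** ASB consumers are identified from the sampling questionnaires, before allocation.
- **That the single-blind label means participants are unaware of their arm.** The masking sentence points to data collectors, and a participant must know of a beverage ban in order to follow it.

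**Conclusion.** The point holds as a minor design weakness. The Protocol places the basal measurements after random assignment, masks only data collectors, and does not withhold the arm from participants until the basal data are complete. Self-reported basal intake could therefore depend on the arm; the document does not show that it does.

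The size is unknown. If change in intake is analysed, the bias is f - d under the present order and f after the reorder, and the direct comparison at week 6 or 12 carries f under either. This rests on three assumptions: the interview follows assignment as the text order suggests, participants could know their arm by then, and the reporting shift is the same at weeks 6 and 12. If the second fails, d = 0 and there is nothing to correct beyond saying so.

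**What to change.** **Participants not yet assigned.** Replace the order in the Protocol with text such as: After consent, the basal blood sample, anthropometry, 24-h recall and food frequency questionnaire are completed, together with the physical activity questionnaire if it is taken at baseline. Only then is the allocation opened and told to the participant.

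**Participants already assigned.** Report, where it can be established, whether the arm was disclosed before or after the basal interview. Alongside any change in intake, also show the direct between-arm comparison of intake at weeks 6 and 12, which does not use the basal value. State that a follow-up reporting shift may remain under either order.

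**Optional check.** Count, by arm, those selected as ASB consumers who report no ASB intake at the basal interview. This is at most a rough descriptive check: it is subject to chance and to differences between the two instruments, and it misses partial under-reporting.

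**Cost.** Close to nothing, since the measurements already planned are taken in a different order. The downside is two baseline procedures within one trial, to be reported with the number of participants under each. The share still reachable is unknown: the Protocol is dated February 2018, the study period runs from February 2017 to October 2018, and no enrolment data are given. If disclosure already follows the basal data in practice, one sentence saying so settles the matter.
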